#### **9.2.7.5 Biochemistry**

If below biochemistry analyses are performed as a part of the local clinical practice, they should be recorded in the eCRF.

- Aspartate aminotransferase (AST)
- Bilirubin
- Creatinine
- Alanine Aminotransferase (ALT)
- Estimated Glomerular Filtration Rate (eGFR)

#### **9.2.7.6 Urinalysis**

If urine dipsticks are used in local clinical practice, the test result for proteins in urine should be recorded in the eCRF.

#### **9.2.7.7 Physical examination**

It is recommended to perform physical examination at every visit. The examination may include:

- General appearance
- Head, ears, eyes, nose, throat, neck
- Respiratory system
- Cardiovascular system
- Gastrointestinal system incl. mouth
- Genito-urinary system
- Musculo-skeletal system
- Central and peripheral nervous system
- Skin
- Lymph node palpation

Findings that exist at the time of enrolment in the study should be reported as medical history, new abnormal findings should be reported as adverse events (AE).

Protocol  
NN7088-4029  
UTN: U1111-1235-6007  
EU PAS No.

~~CONFIDENTIAL~~

Date: 17 April 2020  
Version: 2.0  
Status: Final  
Page: 26 of 49

**Novo Nordisk**

### **9.2.7.8 Adverse event, serious adverse events and adverse events of special interest**

All adverse events (AEs), including serious adverse events (SAEs), either observed by the physician or reported by the patient must be recorded and evaluated by the physician. Adverse events of special interest (AESI), which in the evaluation of safety have a special focus, are listed in section [11.1](#) and [appendix A](#).

At each contact with the site during the study, the patient should be asked about AEs since the last contact. Please refer to [appendix A](#) and section [11](#) for AE, SAE and AESI definitions, collection, recording, and reporting times. AE collection and reporting must be performed after signed informed consent and until a patient's last visit in the study.

Bleeding episodes are not considered adverse events unless the bleeding episode is fatal, life threatening or evaluated by the investigator as possibly caused by the study product. Causes to a bleeding episode may be considered as an AE e.g. an injury.

### **9.2.8 Other assessments**

#### **9.2.8.1 Informed consent**

The date of informed consent must be recorded in the eCRF after having obtained patient's, parent's or LAR's, informed consent, as applicable.

#### **9.2.8.2 Medical history**

The information collected for medical history should include diagnosis and resolution date and be recorded at the baseline visit based on discussion with the patient and/or based on medical records. If a diagnosis is unknown, the description of symptoms should be recorded.

#### **9.2.8.3 Haemophilia treatment and bleed history**

Haemophilia treatment history should be recorded including the number of months on prophylactic/on demand regimen and the used dosing regimen for the preceding 12 months. In case of an emerging inhibitor the brand name of the FVIII product used for prophylaxis and/or episodic treatment should be recorded in the eCRF.

#### **9.2.8.4 Details of Haemophilia**

Details of Haemophilia should be collected with FVIII level from medical history. Previous positive inhibitor status, including transient inhibitors or successful Immune Tolerance Induction (ITI) therapy should be recorded in the eCRF. Known family history of haemophilia should be recorded in the eCRF with "yes" or "no".

#### **9.2.8.5 Demography**

Collected as allowed by local law:

Protocol  
NN7088-4029  
UTN: U1111-1235-6007  
EU PAS No.

~~CONFIDENTIAL~~

Date:  
Version:  
Status:  
Page:

17 April 2020  
2.0  
Final  
27 of 49

**Novo Nordisk**

- Date of birth
- Ethnicity
- Race

#### **9.2.8.6 Concomitant illness**

Definition of concomitant illness: any clinically significant illness that is present at study entry (i.e. at baseline visit/visit 1) including viral infections e.g. human immunodeficiency virus (HIV) and should include diagnosis. If a diagnosis is unknown, the description of symptoms should be recorded.

Any changes from visit 1 in concomitant illness must be recorded at each visit in the eCRF. In case a concomitant illness deteriorates during the study, an adverse event must be recorded and reported according to section [11](#) and [appendix A](#). If the change influences the patient's eligibility to continue the study, the sponsor must be informed.

#### **9.2.8.7 Concomitant medication**

Definition of concomitant medication: any medication other than N8-GP that is taken during the study, including medication reported at baseline visit (visit 1). Any changes in medication must be recorded at each visit in the eCRF.

The information collected for each concomitant medication should preferably include trade name or generic name, indication, start and stop date or continuation. If concomitant medication is taken due to an adverse event this must be listed in the eCRF.

#### **9.2.8.8 Genotype**

If a FVIII genotyping result is available this should be recorded in the eCRF. Genotype result may only be collected upon consent given.

#### **9.2.8.9 Dosing regimen**

The N8-GP dosing regimen at study entry and any changes in regimen during the study, must be recorded in the eCRF, including dosing regimen and date.

The physician should at each visit discuss the haemophilia treatment with the patient. The patient should be asked if the prophylaxis doses of N8-GP were taken as prescribed since last visit, and any deviations from the prescription must be recorded in the eCRF.

The physician should ensure that the patient notes down any treatment relevant details between the visits in his own personal notes/diary. The patient diary (for example national mobile application or personal paper diaries) must be used as a basis in the discussion during the routine visits to the clinic.

Protocol  
NN7088-4029  
UTN: U1111-1235-6007  
EU PAS No.

~~CONFIDENTIAL~~

Date: 17 April 2020  
Version: 2.0  
Status: Final  
Page: 28 of 49

**Novo Nordisk**

### **9.2.8.10 Body measurements**

It is recommended to weigh the patient at each visit and measure the height if the patient is in the age of growing height. The height should be measured without shoes.

### **9.2.8.11 Surgery**

Patients undergoing surgery will be managed according to local clinical practice. For surgery the following data should be recorded in the patient's eCRF, if available:

- Date of surgery
- Indication

## **9.3 Variables**

Data within safety (AEs) will be collected. Data and results from assessments and laboratory analyses according to flow chart will be recorded if performed as part of the routine clinical practice. Consumption of N8-GP will be based on treatment regimen and reported bleeding episodes and will be reported in the electronic Case Report Form (eCRF) system, based on patients own diary.

Ongoing monitoring will ensure that all collected data will be transferred to the eCRF as relevant.

## **9.4 Data sources**

Data and results available in the patients' medical record and from assessments and laboratory analyses performed according to local practice at the participating sites will be recorded in the eCRF. In addition, available information from patients own diary related to treatment, FVIII treatment requiring bleeding episodes and in case a patient is hospitalized should be reported in the patient's record and subsequently in the eCRF by the health care professional. Data sources are eCRFs, paper CRF form (pregnancy in patient's female partner), medical record and laboratory data.

## **9.5 Study size**

The study is planned to include safety follow-up assessments at routine care visits for at least 5 years with 50 patients. The sample size is based on a regulatory request from EMA and no formal sample size calculation was performed.

## **9.6 Data management**

Data management is the responsibility of Data Management at Novo Nordisk. Data management may be delegated under an agreement of transfer of responsibilities to another data management unit within Novo Nordisk or a Contract Research Organisation (CRO).

Protocol  
NN7088-4029  
UTN: U1111-1235-6007  
EU PAS No.

~~CONFIDENTIAL~~

Date: 17 April 2020  
Version: 2.0  
Status: Final  
Page: 29 of 49

**Novo Nordisk**

Novo Nordisk will provide electronic Case Report Forms (eCRFs) for capture of study specific patient data. Instructions for completion and correction of eCRF will be provided.

The only CRF Paper form included in the study is “pregnancy in patient’s female partner”.

The physician must ensure that study specific patient data is entered in the eCRF as soon as possible after the visit and no later than 5 days after.

The physician should ensure that all available data present is registered, and all possible questions answered. If a test/assessment has not been done and will not be available, or if the question is not applicable, it must be indicated according to the instructions for completing eCRFs.

Appropriate measures such as encryption or deletion must be enforced to protect the identity of patients when transmitting data, in all presentations and publications as required by local/regional/national requirements.

The system for Electronic Data Capture (EDC) and support services for the system will be supplied by [REDACTED]. The activities of [REDACTED] will be under the direction and supervision of Novo Nordisk.

An audit trail will be maintained in the EDC application containing as a minimum: identification of the person entering the data, date and time of the entry and reason for the correction, the original entry and the corrected entry.

By signing the affirmation statement/casebook the physician confirms that the information in the eCRF is complete and correct.

If corrections are made by the physician’s authorised staff after the date of the physician’s signature on the affirmation statement/casebook, this must be signed again by the physician.

After the study database is released, site specific eCRF data must be downloaded by site in an electronic readable format of site’s choice. The access to the study specific EDC may subsequently be revoked.

## **9.7 Data analysis**

Novo Nordisk will be responsible for the statistical analyses but may contract a CRO to perform the task.

If necessary, a statistical analysis plan (SAP) may be written in addition to the protocol, including a more technical and detailed elaboration of the statistical analyses. The SAP will be finalised before database lock.

Protocol  
NN7088-4029  
UTN: U1111-1235-6007  
EU PAS No.

~~CONFIDENTIAL~~

Date: 17 April 2020  
Version: 2.0  
Status: Final  
Page: 30 of 49

**Novo Nordisk**

### **9.7.1 Definition of analysis sets**

All safety analyses will be based on the safety analysis set (SAS) where all patients exposed to N8-GP during study period will be included.

### **9.7.2 Statistical methods**

No formal testing of statistical hypothesis will be performed. All data will be presented using descriptive statistics. Categorical data will be summarized by frequency tables while continuous data will be summarized by mean, standard deviation, median, minimum and maximum value.

Subgroup analysis will be presented:

- By age groups (< 6 years, 6 to < 12 years, 12 to < 18 years, 18 to < 65 years, ≥ 65 years)
- By severity of disease (moderate and severe)

Patients who previously developed inhibitors before entering this study might be presented separately if deemed necessary.

#### **9.7.2.1 Primary endpoint**

- Number of Adverse Events (AEs) reported during the study period

The number of AEs reported during the study period will be summarised together with the number of patients with any AE. Furthermore, listings will be provided displaying all AEs.

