**Novo Nordisk**

#### 4.4 Study design

This is a prospective, multinational, non-interventional PASS in patients with moderate or severe haemophilia A. Patients fulfilling the inclusion criteria can participate in the study regardless of previous treatment regimen, allowing inclusion of patients previously exposed to N8-GP and/or other FVIII products.

Patients will be treated with commercially available N8-GP according to local clinical practice at the discretion of the physician.

The total study duration is estimated to be 7 years with a planned recruitment period of approximately 2 years. The aim is to collect data on 50 patients on prophylaxis with N8-GP for at least, but not limited to 5 years. Patients may continue in the study for the total planned study duration allowing active data collection for up to 7 years.

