**Novo Nordisk**

adolescents and adults with severe haemophilia A (FVIII activity  $\leq 1\%$ ). The phase 3 trials documented that N8-GP is efficacious for prophylaxis and treatment of bleeding episodes across all age groups and in providing effective haemostasis during and after major surgical procedures. The median annualized bleeding rate for adolescents and adults was 1.18 and for children 1.95. In children, 82 % of their target joints did not bleed during the main phase of the trial, and children overall also showed an enhanced quality of life. The overall success rate for the first treatment of a bleeding episode evaluated within 8 hours was 88 %.

The general safety profile of N8-GP for the treatment of patients with haemophilia A is well examined through the clinical development programme, where N8-GP was well tolerated and has demonstrated a safety profile in the pivotal phase 3 trial in adolescents and adults, in the paediatric phase 3 trial and the surgery phase 3 trial similar to that of currently approved FVIII products.

The Committee for Medicinal Product for Human use (CHMP) has raised a theoretical concern regarding potential long-term effects of PEG accumulation in organs and other tissues. Based on modelling data and supported by analyses of PEG plasma levels in clinical samples from adolescent/adult and paediatric patients participating in the N8-GP phase 3 trials, plasma steady-state PEG concentrations have been reached in the clinical trial programme without any indication of PEG-related adverse effects to date. The clinical safety of long-term exposure to N8-GP – including evaluation of potential clinical consequences of exposure to 40 kDa PEG in organs and tissues – is yet to be established.

As per guideline, it is a request from the European Medicines Agency (EMA) to collect additional clinical data and to ensure consistency between the outcome from the pre-authorisation clinical trials and those from post-approval local clinical practice use of commercially available product. Therefore, a post-marketing investigation should be performed. Novo Nordisk has received an obligation to conduct a Post-Authorisation Safety Study (PASS) to investigate the potential effects of PEG accumulation in organs and other tissues.

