**Figure 9-1 Study Design**

### 9.1.1 Primary endpoint

Endpoint	Time frame	Unit
Number of Adverse Events (AEs) reported during the study period	From inclusion of the patient until end of study	Count of events

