#### **9.7.2.2 Secondary Endpoint**

- Number of Serious Adverse Events (SAEs) during the study period

Number of Serious Adverse Events (SAEs) reported during the study period will be summarised together with the number of patients with any SAE. Furthermore, listings will be provided displaying all SAEs.

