**Novo Nordisk**

Number of these specific AEs during study period will be summarised together with the number of patients with any of these AEs. Furthermore, listings will be provided displaying all these specific AEs.

- Changes in laboratory parameters during the study period, including hepatic and renal function parameters.

Laboratory parameters will be summarised by visit. Furthermore, change from baseline (visit 1) will be summarised. Listings and individual over time profile plots (where deemed relevant) will be provided displaying laboratory parameters reported during the study period.

- PEG-plasma levels at study entry, after two years and at the end of study

PEG plasma level will be summarised by visit. Listings and individual over time profile plots will be provided displaying PEG plasma level reported during the study period.

- Number of FVIII treatment requiring bleeding episodes reported during the study period

Number of FVIII treatment requiring bleeding episodes reported during the study period will be summarised. Furthermore, listings will be provided displaying all FVIII requiring bleeding episodes.

Definition of a bleeding episode: Multiple bleeding locations occurring during the same event (e.g., due to a bicycle accident) or at the same time point will be counted as one bleeding episode. A bleeding which occurs within 72 hours after stopping treatment of a previous bleeding event at the same or a subset of the same anatomical location(s) is considered a re-bleed, and is not a new bleeding episode. If a bleeding event occurs in the same location later than 72 hours after stopping treatment of a previous bleeding event it is considered a new bleeding episode.

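### AEs, SAEs, organ-specific AEs and bleeds are fixed as raw counts, with no person-time denominator or interval, although follow-up is unequal by design

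*Protocol*

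**What the plan says.** Protocol 9.1.1 gives the unit of the primary endpoint as "Count of events" and its time frame as "From inclusion of the patient until end of study". Sections 9.1.2 and 9.1.3 give the same unit for SAEs, for hepatic or renal AEs, for neurological AEs and for bleeds that need FVIII treatment.

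The analysis sections follow from this:

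- Primary endpoint (9.7.2.1): "The number of AEs reported during the study period will be summarised together with the number of patients with any AE".
- Secondary endpoint (9.7.2.2): "Number of Serious Adverse Events (SAEs) reported during the study period will be summarised together with the number of patients with any SAE".
- Organ-specific AEs (9.7.2.3): the number of events and the number of patients with any such event.
- Bleeds (9.7.2.3): "Number of FVIII treatment requiring bleeding episodes reported during the study period will be summarised". The only addition is listings; the number of patients with a bleed is not mentioned.

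Section 9.7.2 states that "No formal testing of statistical hypothesis will be performed" and limits the summaries to frequency tables and mean, SD, median, minimum and maximum. It also plans results for five age groups and two severity groups.

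On follow-up, section 4.4 plans about 2 years of recruitment within a 7-year study and adds: "Patients may continue in the study for the total planned study duration allowing active data collection for up to 7 years". The end-of-study visit is tied to one common last-visit date (9.2.6.4). Patients may withdraw at any time (9.2.5), all exposed patients are analysed (9.7.1), and follow-up is meant to continue after N8-GP is stopped (9.1). Interim results are planned for periodic safety reports, for the 5-year renewal and at about 2.5 years (9.7.3).

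**The concern.** An event count depends on the event rate and on the time during which events could be recorded. When that time differs between patients, subgroups or data cuts, the count alone does not say how often events occur. The number of patients with any event has the same weakness, because it too grows with follow-up.

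Three uses of the results are affected. First, successive interims and the final report will show rising counts that say nothing about whether risk has changed. Second, the background in section 7 describes the regulator's request as one "to ensure consistency between the outcome from the pre-authorisation clinical trials" and those from practice, and it quotes phase 3 bleeding as annualised rates; a total number of bleeds has no common scale with these. Third, section 7 says the study was imposed because of possible PEG accumulation in organs and tissues. A likely key result is few or no hepatic, renal or neurological events, and the plan contains no statement of the rate that such a result would rule out.

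**Working it through.** The protocol states no rate, precision or power to reproduce. Its size of 60 enrolled and 50 completers rests on a regulatory request (9.2.1, 9.5).

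**Inputs from the protocol:** first visit 3 June 2020 and last visit 3 June 2027, 7 years (section 6); recruitment about 2 years (4.4); 60 enrolled, 50 completing (9.2.1); interim at about 2.5 years (9.7.3); median annualised bleeding rates 1.18 and 1.95 (section 7).

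**Assumptions, not in the protocol:** even accrual over the 2 years; a constant event rate.

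**Follow-up per completer.** From 7 − 2 = 5 years to 7 years, mean 6 under even accrual. At one rate, the expected count differs by 7/5 = 1.4 between the latest and earliest entrants. Against a patient who leaves after 1 year the ratio is 7/1 = 7.

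**Patient-years (PY).**

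| Cut | Calculation | PY |
|---|---|---|
| 2.5-year interim, no drop-out | 60 × (2.5 − 1) | 90 |
| Completers at the 5-year minimum | 50 × 5 | 250 |
| End, attrition to 50 of 60 at 6 years (exponential) | 60 × 5.48 | about 329 |
| End, no drop-out | 60 × 6 | 360 |

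From interim to end the count rises by 329/90 = 3.7 to 360/90 = 4.0 times at an unchanged rate.

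**Patients with any event**, 1 − exp(−rate × T). At an assumed 0.1 events per year this is 9.5% at 1 year, 39.3% at 5 years and 50.3% at 7 years.

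**Bleeds.** Treating 1.18 per year as a mean rate (it is a median, so this is illustrative), the total is 1.18 × 90 = 106 at the interim and 1.18 × 360 = 425 at the end. Both describe the same bleeding pattern, and neither can be compared with 1.18 without the denominator.

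**Zero events.** The exact two-sided 95% Poisson upper limit is −ln(0.025)/PY = 3.689/PY:

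- 90 PY: 4.1 per 100 PY
- 250 PY: 1.48 per 100 PY
- 360 PY: 1.02 per 100 PY

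Per patient, 0 of 60 gives 1 − 0.025^(1/60) = 6.0%.

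**A small non-zero count.** Five events on 250 PY is 2.00 per 100 PY, exact 95% interval 0.65 to 4.67.

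**The case against.** The strongest reply is that this is a descriptive, single-arm study without a comparator, and that exposure adjustment and descriptive intervals are often left to a statistical analysis plan. Saying that events will be summarised does not forbid rates. This stands in part. However, section 9.7 makes such a plan optional and gives it technical elaboration, while the protocol itself fixes the unit of the endpoints and the list of summary statistics.

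A reader might infer several stronger points that the documents do not support:

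- **That zero events could not be interpreted at all.** The number of patients with any AE or SAE is planned, so 0 of 60 can be bounded at 6.0%. Zero is also implausible for all AEs or for bleeds. The gap is the missing bound per unit of time for rare, organ-specific events.
- **That unequal follow-up drives the results.** Among completers the spread is at most 1.4-fold. Subgroup counts mislead only if follow-up differs between subgroups, and nothing says that it does.
- **That nearly every patient will have an AE whatever the drug does.** At an assumed 0.5 to 1 AE per year, equal for all patients, 95.0% to 99.8% have one by 6 years. If rates vary between patients (negative binomial, dispersion 1), 1 − 1/(1 + mean) with means 3 and 6 gives 75% and 86%. The protocol states neither the rate nor its spread.
- **That comparison with the phase 3 trials is the study's purpose.** Sections 7 and 8.1 give the purpose as long-term safety. Consistency with the earlier trials is background to the regulator's request, bleeding is exploratory, and no formal comparison with 1.18 or 1.95 is planned.

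Section 9.9 concedes that routine data collection may affect the amount of data and its interpretation, but it does not address unequal follow-up time.

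**Conclusion.** The point holds as one of interpretability and should be fixed; it is not bias in a test, since none is planned. As written, the plan yields counts that rise about 3.7- to 4-fold between the 2.5-year interim and the end with no change in risk, that have no common scale with the annualised rates quoted in the background, and that leave few or no organ-specific events without a stated excluded rate. That rate would be about 1.5 to 1.0 per 100 patient-years for zero events in 250 to 360 patient-years. The 5-to-7-year range follows from the protocol's dates. The patient-year totals for the interim and the end rest on even accrual of 60 patients, and the comparisons of counts on a constant rate.

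**What to change.** In 9.1.1 to 9.1.3 and 9.7.2.1 to 9.7.2.3, keep the counts and the planned numbers of patients with any event, and add:

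- The event rate per patient-year with a 95% confidence interval, at each interim and at the end, and descriptively by subgroup. Use an exact Poisson interval for rare or zero events and an interval robust to overdispersion for recurrent AEs overall. Models within subgroups are not needed; with about 60 patients in five age groups they are unlikely to be stable.
- Individual annualised bleeding rates, reported as mean and median, so that they are on the scale of the medians in section 7.
- One time base for numerator and denominator. Total observation time should be the main measure, because the endpoints count events to end of study. Events on N8-GP over time on N8-GP can be a supplement. Dividing all events by N8-GP exposure alone would be wrong, because follow-up continues after N8-GP is stopped (9.1).

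The cost is about a paragraph of wording and a little programming. Consent date (9.2.8.1), dated regimen changes (9.2.8.9) and an end-of-study form (9.2.6.4) are already collected, and descriptive intervals do not conflict with the absence of formal testing. The downside is that wide intervals become visible.
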